2.4 Objectives and Purpose

The ultimate goal of this study is to determine how effective SSI is in reducing post-operative pain in patients with lower extremity long bone fractures and to determine how that reduction in post-operative pain impacts a patient's hospital stay in the short term and their use of narcotics during the treatment period. Primary outcomes measures will be reported and observed pain scores and narcotic use. VAS and APS-POQ will be used to measure pain scores. While it is expected that the greatest benefit of the SSI will be seen in the first day or two after surgery it is possible that there will be an overall reduction in long-term narcotic use. Secondarily, function/rehabilitation, length of stay, and complications may be impacted by the intervention.

CONFIDENTIAL

This material is the property of the NYU School of Medicine and Langone Medical Center. Do not disclose or use except as authorized in writing by the study sponsor

Interventional Template Version: 28 APR 2017

3 Study Design and Endpoints

Cohort A: Spinal Anesthesia	ARM 1: Experimental	Sample Size: 100	SSI
	ARM 2: Control	Sample Size: 100	No intervention

Cohort B: General Anesthesia	ARM 1: Experimental	Sample Size: 100	SSI
	ARM 2: Control	Sample Size: 100	No intervention

3.1 Description of Study Design

The researchers will use NYU admission records, emergency room records, orthopedic consult records, and immediate care records to identify patients eligible for participation in the study. Orthopedic residents and authorized researchers will consent and enroll patients pre-operatively.

Subjects with a qualifying fracture will be randomized to either the SSI or control group. Subjects in the SSI group will receive a peri-incisional injection of 40cc 0.25% bupivacaine (marcaine), 5 mg morphine sulfate (duramorph) (1 mg/cc, 5 cc total), and 30 mg of ketorolac (30 mg/cc, 1 cc total) into soft-tissue and musculature surrounding the fracture site and 0.25% Bupivacaine (Marcaine) 10 mL into the subcutaneous tissue surrounding the surgical incision. The control group will receive no injection. The injection will be administered by the subjects NYU orthopedic surgeon, all of whom are familiar with the technique. The patient will be blinded to if a medication is being injected. Subjects will not receive ketorolac if they have kidney disease or a history of allergy to NSAIDS or aspirin. The dose of ketorolac will be reduced to 15 mg (30 mg/cc, 0.5cc total) in subjects older than 65 years of age, in subjects with a history of peptic ulcer disease, a CrCl of 30 to 50 ml/min, or subjects with diabetes. These modifications are recommended by the manufacturer and are used in standard practice. A sub group analysis will be done on patients who receive this lower dosage to see if it has an impact on the data.

After initial recruitment, subjects' pain will be assessed via visual analog scale (VAS) by nursing staff on a q4h basis. A standardized regimen of pain medication will be given to all subjects who are enrolled. Pre-operatively subjects will receive acetaminophen 1gm oral (every 6-8 hours, not to exceed 4gm daily) and meloxicam 15mg oral once daily. Post-operatively, subjects will receive acetaminophen 1gm oral (every 6-8 hours, not to exceed 4gm daily), ketorolac 30mg injection, once daily in AM, starting POD 1(15mg for patients >65 years of age and/or renal impairment), and pregabalin (Lyrica) 50mg oral every 8 hours (held for sedation). Ice PRN for mild pain, tramadol 50mg oral every 8 hours PRN for moderate pain, and tramadol 100mg oral every 8 hours PRN for severe pain. Oxycodone 5mg oral every 6 hours PRN will be given for breakthrough pain.

Physical therapy records with regards to ambulation distance and exercise endurance will be examined. Daily assessments of pain via VAS will be obtained by the nursing staff as per standard protocol. APS-POQ form will be given on POD1.

After discharge subjects will receive a 7-10 day prescription for acetaminophen 1000mg every 8 hours, meloxicam 15mg oral once daily, and tramadol 50mg oral, every 4-6 hours, PRN (12 tablets to be dispensed). Subjects will call the provider to request refills as needed.

CONFIDENTIAL

This material is the property of the NYU School of Medicine and Langone Medical Center. Do not disclose or use except as authorized in writing by the study sponsor

Interventional Template Version: 28 APR 2017

[figure not shown]
After discharge the research staff will call the subjects up to every other day for the first week, twice in the second week, once weekly for the third and 4th weeks and then monthly after discharge to ascertain pain level, reported narcotic usage, and functional status. Research staff will verify documented narcotic refills through epic and pharmacy records. Four to eight weeks after injury subjects will complete a SMFA as well as another APS-POQ form over the phone with a trained interviewer.

	Pre-op	Post-op: Inpatient	Post-op: Discharge
Standing	Acetaminophen 1gm, oral (every 6-8 hours, not to exceed 4gm daily, review liver function prior to administration)	Acetaminophen 1gm, oral (every 6-8 hours, not to exceed 4gm daily, review liver function prior to administration)	Acetaminophen 1gm, oral (every 6-8 hours, not to exceed 4gm daily, review liver function prior to administration)
	Meloxicam 15mg oral, once daily	Ketorolac 30mg inj, once daily in AM, starting POD1 (15mg>65 years of age and/or renal impairment) Pregabalin (Lyrica) 50mg, oral every 8 hours (hold for sedation)	Meloxicam 15mg oral, once daily
Mild		Ice Therapy PRN (alternating 15 min on/off for skin evaluation)	
Moderate		Tramadol 50mg oral, every 8 hours, PRN	
Severe		Tramadol 100mg, oral, every 8 hours, PRN	
Breakthrough		Oxycodone 5mg, oral every 6 hours, PRN	Tramadol 50mg oral, every 4-6 hours, PRN (12 tablets to be dispensed)

CONFIDENTIAL

This material is the property of the NYU School of Medicine and Langone Medical Center. Do not disclose or use except as authorized in writing by the study sponsor
Interventional Template Version: 28 APR 2017

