4.2 Exclusion Criteria

An individual who meets any of the following criteria will be excluded from participation in this study:

1. Pregnant women
2. Treatment with Arthroplasty
3. Patients who receive a peripheral nerve block
4. Patients who receive intra-op or post-op ketamine
5. Patients with concomitant TBI or MR
6. Polytrauma patients
7. Pathologic Fractures
8. Patients with a contraindication to any of the medications on the study list due to other medical problems such as renal or liver disease or due to allergy/intolerance
9. Patients with prior extremity weakness resulting from stroke or other neurological condition
10. Prior or current history of narcotic use
11. Patients with advanced dementia
12. NYUMC Students, Residents, Faculty

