6.4 Enrollment/Randomization/Masking Procedures

As per standard of care, an anesthesiologist will determine if subjects receive general or spinal anesthesia. Within these groups subjects will randomized to receive a SSI or no intervention. Randomization will be done via redcapautomated computer randomization. After randomization the surgical team will be informed which group the patient has been randomized into.

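### The reduced-ketorolac subgroup is defined by a dose that only the injection arm can receive, and no comparator is given; it should be defined in both arms by the baseline criteria that trigger the reduction

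*Combined protocol and SAP*

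**What the plan says.** Section 3.1 describes the injection for the SSI arm and says of the other arm: "The control group will receive no injection". It then modifies the ketorolac component in the injection:

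- Reduced for age: "The dose of ketorolac will be reduced to 15 mg (30 mg/cc, 0.5cc total) in subjects older than 65 years of age".
- Reduced for other conditions: "in subjects with a history of peptic ulcer disease, a CrCl of 30 to 50 ml/min, or subjects with diabetes".
- Omitted: "Subjects will not receive ketorolac if they have kidney disease or a history of allergy to NSAIDS or aspirin".

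The subgroup sentence closes that paragraph: "A sub group analysis will be done on patients who receive this lower dosage to see if it has an impact on the data".

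The next paragraph of 3.1 gives the post-operative regimen for both arms, which includes "ketorolac 30mg injection, once daily in AM, starting POD 1(15mg for patients >65 years of age and/or renal impairment".

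Section 4.2 excludes "Patients with a contraindication to any of the medications on the study list due to other medical problems such as renal or liver disease".

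Section 6 does not mention the subgroup. Section 6.2 gives no comparator, model term or interaction test for it, and Section 6.3 gives no size or power. The only stratifying factor for randomisation in Section 6.4 is type of anesthesia: "Within these groups subjects will randomized to receive a SSI or no intervention". Among the baseline data in Section 6.2.1, age and diabetes are named; creatinine clearance and ulcer history are not.

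**The concern.** Membership of the subgroup depends on something that happens after randomisation and in one arm only. No control can receive a lower dose of an injection that controls do not get, so the definition as worded supplies no randomised comparison.

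An analyst left with that wording has two obvious contrasts. The first is low-dose against full-dose patients within the SSI arm. That is not randomised: it sets patients who are older, diabetic, renally impaired or have had an ulcer against everyone else. The second is low-dose SSI patients against all controls, which adds a case-mix difference to the SSI effect. Either could show a difference in opioid use or pain that has nothing to do with the ketorolac dose.

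The post-operative regimen adds to the difficulty. Post-operative ketorolac is also lowered for age over 65 and/or renal impairment, so in many of the same patients the injected and later doses fall together. At stake is a published statement about whether the lower dose matters, resting on a contrast that cannot show it.

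**Working it through.** The plan states no size, effect or power for this subgroup, so there is no figure of its own to reproduce. The structural point follows from the text; the arithmetic only shows scale.

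**Which dose is meant.** The subgroup sentence directly follows the reductions of the injected dose. The post-operative regimen, which controls also receive, appears only in the next paragraph. The natural reading is the injected 15 mg.

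**Inputs.**

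- SD 25 mg/day of morphine equivalents: Section 6.3, taken here as the within-group SD.
- 200 SSI patients: the Section 3 table, 100 in each of two anesthesia cohorts.
- 300–350 evaluable of 400: Section 4.6. The lower end is about 150 per arm if losses are equal.
- Two-sided 5% level: Section 6.3 gives 0.05; two-sided is assumed.
- Share f of patients meeting a reduction criterion: not in the documents. 70% is assumed for the first illustration and 30–70% for the fix.
- Difference b in daily opioid use between patients who do and do not meet the criteria, unrelated to the injection: not in the documents. 3, 5 and 10 mg/day are assumed, in either direction.

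**Low versus full dose within the SSI arm, with no true dose effect.** The contrast is biased by the whole of b. With SE = 25 × √(1/n_low + 1/n_full) and z = b/SE, the chance of p < 0.05 is Φ(z − 1.96) + Φ(−z − 1.96).

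- 200 SSI patients, 140 v 60: SE = 25 × √(1/140 + 1/60) = 3.86.
- 150 SSI patients, 105 v 45: SE = 25 × √(1/105 + 1/45) = 4.45.

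| b (mg/day) | z, 200 patients | Chance | z, 150 patients | Chance |
|---|---|---|---|---|
| 3 | 0.78 | 12% | 0.67 | 10% |
| 5 | 1.30 | 25% | 1.12 | 20% |
| 10 | 2.59 | 74% | 2.25 | 61% |

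**Low-dose SSI versus all controls.** If the controls contain the same share f of such patients, their mean already carries f × b, so the case-mix bias is (1 − f) × b. At f = 0.7 that is 0.9, 1.5 or 3 mg/day; at f = 0.5 it is half of b. It is smaller, but it is added to the SSI effect and cannot be separated from it.

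**Stratum defined at baseline in both arms.** Patients who meet the criteria are then compared with patients who meet them, and b cancels. The difference detectable with 80% power is 2.80 × SE (1.96 + 0.84), with SE = 25 × √(2/n_low) within the stratum and 25 × √(2/n_low + 2/n_full) for the interaction, n being per arm.

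| Per arm | f | SSI v control in stratum (mg/day) | Interaction (mg/day) |
|---|---|---|---|
| 200 | 30% | 12.8 | 15.3 |
| 200 | 50% | 9.9 | 14.0 |
| 200 | 70% | 8.4 | 15.3 |
| 150 | 30% | 14.8 | 17.6 |
| 150 | 50% | 11.4 | 16.2 |
| 150 | 70% | 9.7 | 17.6 |

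The effect within the stratum can be estimated usefully against the 15 mg/day assumed in Section 6.3. The interaction is detectable only if it is about as large as that whole effect.

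**The case against.** The best defence is that Section 3.1 names no comparator, so it does not commit the sponsor to a confounded one. The sentence could mean reduced-dose SSI patients against controls who meet the same criteria. It could also mean repeating the main analysis with and without the reduced-dose patients, in the spirit of the sensitivity analyses in Section 6.1. The second reading makes no claim about dose. This stands in part. A reader might infer that the plan will report a case-mix difference as a dose effect, but the documents describe no such analysis. A reader might also infer that no control counterpart can exist. That goes too far: controls who meet the criteria will be enrolled; the plan simply does not use them. What remains is that the written definition picks out patients in one arm by dose received, and nothing in Section 6 corrects it.

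A second objection is that the percentages depend on an invented difference in opioid use. That also stands. The 74% is not an expected error rate: it needs a 10 mg/day difference and all 200 SSI patients, and the table shows how quickly the figure falls.

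A third is that the remedy does not answer the dose question either. True: dose stays tied to the criteria in every patient, so no analysis of this trial can separate 15 mg from 30 mg. The remedy replaces that question with one the randomisation can answer.

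Finally, this is one exploratory sentence, touching no primary endpoint. That bears on the weight of the point, not on its correctness.

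**Conclusion.** The point holds as a defect of definition. As worded, the subgroup exists only in the SSI arm, has no stated comparator, and is selected by age over 65, ulcer history, creatinine clearance of 30–50 ml/min and diabetes. The two most obvious contrasts would mix dose with case mix, and the parallel reduction of post-operative ketorolac adds to this.

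The size is uncertain. With SD 25 mg/day, a 70% share and no true dose effect, the chance of a spurious significant low-versus-full contrast runs from about 10% to 74% over assumed differences of 3–10 mg/day and 150–200 SSI patients. The share and the difference are assumptions without a source in the documents.

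It would be wrong to conclude that the trial's main result is compromised. The primary SSI-versus-control comparison does not depend on this subgroup. The change is worth making because a better definition is available at little cost.

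**What to change.** In Sections 3.1 and 6.2, replace the definition by dose received with one that applies to both arms:

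1. Define the stratum by the baseline criteria that trigger the reduction, assessed before randomisation for every participant.
2. Add creatinine clearance and peptic ulcer history to the data in Section 6.2.1 and record them for controls too.
3. State how patients who receive no ketorolac are classified. First reconcile the renal statements: 3.1 omits the injected drug for kidney disease and reduces it over a range of creatinine clearance, the post-operative regimen reduces it for renal impairment, and 4.2 excludes contraindications due to renal disease.
4. Estimate SSI versus control within each stratum with 95% confidence intervals, and test the treatment-by-stratum interaction. Label this exploratory, since the interaction detectable at 80% power is about 14–18 mg/day for shares of 30–70%.
5. State that the result describes the SSI effect in patients who qualify for the reduced dose and is not a causal comparison of doses.

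The cost is a few sentences and two baseline items recorded in both arms. Neither sample size nor randomisation changes.

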3.2 Schematic of Study Design

4 Study Enrollment and Withdrawal

4.1 Inclusion Criteria

In order to be eligible to participate in this study, an individual must meet all of the following criteria:

1. Age above 18
2. Lower extremity fracture including femoral neck, intertrochanteric, sub-trochanteric, and femoral shaft fracture

CONFIDENTIAL

This material is the property of the NYU School of Medicine and Langone Medical Center. Do not disclose or use except as authorized in writing by the study sponsor
Interventional Template Version: 28 APR 2017

3. English Speaking as primary or native language

4.2 Exclusion Criteria

An individual who meets any of the following criteria will be excluded from participation in this study:

1. Pregnant women
2. Treatment with Arthroplasty
3. Patients who receive a peripheral nerve block
4. Patients who receive intra-op or post-op ketamine
5. Patients with concomitant TBI or MR
6. Polytrauma patients
7. Pathologic Fractures
8. Patients with a contraindication to any of the medications on the study list due to other medical problems such as renal or liver disease or due to allergy/intolerance
9. Patients with prior extremity weakness resulting from stroke or other neurological condition
10. Prior or current history of narcotic use
11. Patients with advanced dementia
12. NYUMC Students, Residents, Faculty

4.3 Vulnerable Subjects

No vulnerable populations will be intentionally solicited. It is possible that employees, economically disadvantaged persons and students will be solicited in the course of enrollment however no one will be specifically recruited for these reasons and no one with ties to the NYU Orthopedics department or NYU School of Medicine will be eligible for participation.

4.4 Recruitment and Consent

This study will utilize EPIC to identify subjects and redcap to manage and store relevant data. EPIC will be used to identify patients who have been admitted with the injury types described above and who meet the inclusion and exclusion criteria. The PHI that will be seen will include their name, diagnosis, medical record number, age, and telephone number. This is the minimum necessary to identify patients over time and to determine if they are eligible for the study. Approved study team members will handle recruitment efforts. Patients confidentiality will be maintained as all study team members will have gone through CITI training and data will be kept in a secure manner as detailed below. This recruitment search will be done daily.

All orthopedic surgeons at NYU will be notified of the study prior to initiation. If the treating physician has a patient who is recruited and consented they will be notified via sendsafe email.

There will be no recruitment materials used in the study. All recruitment will be done face to face.

If a subject requests information regarding opting out of further recruitment for all research, subjects will be directed to contact [contact] or [name].

Process of Consent

The consent for participation will be collected during the hospital stay on day one by a study team member. The study team member may or may not be a part of the patients care team. Due the rapid nature of trauma surgery, patients will have a few hours from the time of recruitment to the time of surgery to decide if they want to participate in the study. This will be done in privacy in the patient's hospital room or other private location such as a patient conference room. Extensive discussion of risks and possible benefits of participation will be provided to the participants and their families. Consent forms will be IRB-approved and the participant

CONFIDENTIAL

This material is the property of the NYU School of Medicine and Langone Medical Center. Do not disclose or use except as authorized in writing by the study sponsor

will be asked to read and review the document. The investigator will explain the research study to the participant and answer any questions that may arise. All participants will receive a verbal explanation in terms suited to their comprehension of the purposes, procedures, and potential risks of the study and of their rights as research participants. Participants will have the opportunity to carefully review the written consent form and ask questions prior to signing. The participants will have the opportunity to discuss the study with their surrogates or think about it prior to agreeing to participate. The participant will sign the informed consent document prior to any procedures being done specifically for the study. The participants may withdraw consent at any time throughout the course of the trial. A copy of the signed informed consent document will be given to the participants for their records. The rights and welfare of the participants will be protected by emphasizing to them that the quality of their medical care will not be adversely affected if they decline to participate in this study.

A website (<https://nyuorthoresearch.com/>) has been created to assist study team members with subject enrollment and consent form access. The website will be updated every six months. Only IRB-approved study documents will be uploaded on the website. The IRB-approved study team members may use this website to download a pdf version of the consent form, which can then be printed and signed by the study subject. The website will altogether be used as a tool for IRB-approved study team members to access clean study documents. A link on the website will also direct the study team member to a redcap survey that will link directly to the redcap project to allow for direct entry of the patient's information for the study. After entering the patient information into the redcap survey, the study team member will not be able to re-download the patient's protected health information from the website and no subject protected health information will be stored on the website. This process is necessary to allow for IRB-approved study team members to enroll subjects while appropriately limiting access to the protected health information in the redcap project as outlined in this protocol. Please see section 10.5 for further information on security of the website.

After obtaining consent, the IRB-approved study team members will either place the consent in a locked research box available at the participating hospitals locked resident room or place it in the locked office of the PI. Signed consents placed in a secure research lockbox will be collected by IRB-approved study team members and placed in the locked office of the PI.

Ultimately, a copy of the signed informed consent document will be stored in the subject's research record. The consent process, including the name of the individual obtaining consent, will be thoroughly documented in the subject's research record.

Subject Capacity

All subjects will be assessed for capacity to give informed consent by the study team member, all of whom are physicians. Capacity will be assessed through the subjects' ability to express understanding of the information presented to them, their ability to express a choice, their appreciation of how this is relevant to them, and reasoning about how the study might impact them and others. As specific for capacity testing, the patient must be able to answer the following questions:

- Understanding: "Can you tell me in your own words what I just said about the study?"
- Expressing a choice: "Based on what we've just discussed about the study, what would you choose?"
- Appreciation: "Regardless of what your choice is, do you think that it is possible the medication can benefit you?" and "Regardless of what your choice is, do you think it is possible the medication can harm you?"
- Reasoning: "How could participating in the study affect you?"

Additionally, the study team member will assess mental status by asking the patient for their full name, location, and the date. This is a standard practice to ensure a patient is alert and oriented to person place and

CONFIDENTIAL

This material is the property of the NYU School of Medicine and Langone Medical Center. Do not disclose or use except as authorized in writing by the study sponsor

Interventional Template Version: 28 APR 2017

time. Capacity testing and the mental status exam will help to reduce the risk of influencing a patient whose judgement may be altered due to opiates or emotional stressors from trauma. As listed in exclusion criteria, those with dementia will be excluded from the study.

All study team members will be physicians, trained in obtaining informed consent.

Subject/Representative Comprehension

The subject themselves will have to clearly state back the basic goals of the study (i.e. to look at the effect of different medications on bone healing) and state that they are willing to participate. This may be done in English or in their primary language with an interpreter.

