SAE	Serious adverse event
IV	Intravenous
PO	Taken orally
PRN	Taken as needed
TID	Taken three times per day
Q4h	Taken every four hours
CI	Confidence interval
SD	Standard deviation; a parameter which characterizes a population distribution
SE	Standard error
SSI	Surgical Site Injection
ANOVA	analysis of variance; a linear model
NSAID	Non-steroidal anti-inflammatory drug
LOS	Length of Stay

CONFIDENTIAL

This material is the property of the NYU School of Medicine and Langone Medical Center. Do not disclose or use except as authorized in writing by the study sponsor
Interventional Template Version: 28 APR 2017

Protocol Summary

Title	Effects of a Surgical Site Injection on Pain Scores and Narcotic Use after Orthopedic Trauma Surgery
Short Title	Understanding and Improving post-operative Pain in the Fracture Population
Brief Summary	This is a phase I, randomized, single-blind, placebo-controlled, single-center study of the effects of surgical site injection on pain and narcotic utilization in participants who undergo surgery for lower extremity fractures. 400 participants with lower extremity fractures who are admitted for operative fixation will be included in the study. Participants will be randomized to receive either a pain cocktail injection around the fracture site and surrounding tissues or control (no injection). An analysis of pain scores, rehabilitation progress, length of stay, narcotic utilization, and satisfaction scores will be performed.
Phase	Clinical study phase 1
Objectives	To understand the effect of surgical site injections of post-operative pain control
Methodology	phase I, randomized, single-blind, placebo-controlled, single-center study
Endpoint	10mg change in narcotic utilization daily or 15mm change in VAS
Study Duration	4 years
Participant Duration	3 months
Duration of IP administration	Once during surgery
Population	400 participants with peritrochanteric fractures
Study Sites	NYU Langone (Kimmel, Tisch, Langone Orthopedic Hospital, Lutheran)
Number of participants	400
Description of Study Agent/Procedure	Peri-incisional injection of 40cc 0.25% bupivacaine, 5 mg morphine sulfate (1 mg/cc, 5 cc total), and 30 mg of ketorolac (30 mg/cc, 1 cc total) into soft tissue and musculature surrounding the fracture site and 0.25% Marcaine 10 mL into the subcutaneous tissue surrounding the surgical incision.
Reference Therapy	Reference is a control
Key Procedures	Surgical Site injection

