administration which showed a statistically significant difference in pain scores and narcotic usage administration between the two groups on post-operative day one, with those who received SSI having less pain and narcotic usage. What remains to be seen is how these interventions impact rehabilitation and narcotic usage in the long-term.

After sustaining hip or other lower extremity fractures, roughly 50% of patients experience persistent pain at the fracture site. Their perception of this pain and the limitations that they suffer because of it may be influenced by their perioperative pain control and expectations regarding their pain and ability to return to normal living⁶. The goal of this study is to not only impact the acute use of narcotics during the inpatient admission but to impact the long term outcome of fracture pain on long-term functional outcomes for these patients.

At our institution pre-op fracture pain management was not standardized and had been a combination of morphine, fentanyl, dilaudid, and oxycodone given in the emergency and in-patient setting. Post-operatively, oxycodone-acetaminophen 5-325mg and 10-325mg were given for moderate and severe pain every four hours respectively with a dose of oxycodone-acetaminophen 5-325 for breakthrough pain. Adjuncts to these medications such as acetaminophen, tramadol, ketorolac, ofirmev, gabapentin, pregabalin were given inconsistently and often not at all. Starting November 2018 our institution began a new post-op pain medication protocol. In this study a standardized regimen of pain medication will be given to all patients who are enrolled to eliminate this as a potential confounder. The ultimate goal of this study is to diminish the use of post-op narcotics and reduce post-operative pain through the use of an intra-operative SSI.

Rationale for Drug Selection and Route of Administration

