6.2.1 Baseline Descriptive Statistics

The following patient data will be recorded: age, gender, height, weight, date of admission, date of discharge, injury time, injury type, laterality, surgical approach, implants used, duration of surgery, time to union, contamination, ASA, comorbidities (smoking, cardiac history, diabetes, etc.), CBC (WBC, PCV, HGB, RBC, indices, platelet count, differential), and medications.

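### The mandatory comprehension check in section 4.4 names a goal (bone healing) that is not an aim or endpoint of this trial, and its interpreter allowance conflicts with inclusion criterion 3

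*Combined protocol and SAP*

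**What the plan says.** The comprehension paragraph at the end of section 4.4 (Recruitment and Consent) sets a requirement: "The subject themselves will have to clearly state back the basic goals of the study". A parenthesis introduced by i.e. then supplies the goal: "to look at the effect of different medications on bone healing". The subject must also say that he or she is willing to take part. On language, the paragraph adds: "This may be done in English or in their primary language with an interpreter".

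Elsewhere the document describes a different purpose:

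- Protocol Summary, Objectives: "To understand the effect of surgical site injections of post-operative pain control".
- Section 2.1: "The ultimate goal of this study is to diminish the use of post-op narcotics and reduce post-operative pain".
- Section 2.4: "Primary outcomes measures will be reported and observed pain scores and narcotic use".

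On eligibility, criterion 3 in section 4.1 reads "English Speaking as primary or native language". The lead-in to that list says an individual has to satisfy every criterion.

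**The concern.** The paragraph is an instruction to the staff who take consent, not background. It is also the one comprehension step for which the protocol writes down the content expected in the answer, and that content does not describe this trial. If the text is taken at its word, a patient who correctly says that the study concerns pain and narcotic use has not given the goal the protocol states.

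The setting makes an accurate check worth having. Section 4.4 allows patients only a few hours between recruitment and surgery, and it acknowledges that opiates and the stress of trauma may affect their decisions. What is at stake is participant protection and a consent record that matches the trial.

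The interpreter sentence raises a separate, smaller problem: two parts of the protocol give staff conflicting signals about whether a patient who needs an interpreter can be in the study.

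**Working it through.** No arithmetic applies. The check is a comparison of the text in two parts.

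**1. The goal in the check against the goal of the trial**

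| Place | What it gives as purpose or outcome | Bone healing? |
|---|---|---|
| Protocol Summary, Objectives | Post-operative pain control | No |
| 2.1 Background | Less narcotic use, less post-operative pain | No |
| 2.2 Aims 1 to 3 | Pain; narcotic usage; function, length of stay and complications | No |
| 2.3 Hypotheses | Pain, narcotic usage, function, length of stay, complications | No |
| 2.4 Objectives | Pain scores and narcotic use as primary outcomes | No |
| 6.2 Primary endpoints | Amount and duration of narcotic use, reported pain | No |
| 6.2 Secondary endpoints | Length of stay, physical therapy progress, long-term narcotic use, discharge location, refills, falls, adverse events | No |
| 6.2.1 Recorded patient data | "duration of surgery, time to union, contamination, ASA", among other items | Recorded only |
| 4.4 Comprehension check | Effect of different medications on bone healing | **Yes, as the goal** |

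Two places come near to healing, and neither rescues the parenthesis. Time to union in 6.2.1 is a variable to be recorded, with no aim, hypothesis or analysis attached to it. The complications in 2.2 and 2.3 are left open-ended, so a healing problem could be counted among them. That would make it one item within a third-ranked aim, not the basic goal of the study.

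The parenthesis also misdescribes the comparison. It speaks of different medications, whereas section 3.1 compares an injection with no injection, on top of one standardized pain regimen given to everyone enrolled.

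The choice of i.e. matters. It presents bone healing as the goal itself, whereas e.g. would have offered it as one illustration among several.

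**2. The interpreter sentence against criterion 3**

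There are three kinds of patient:

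| Patient | Meets criterion 3? | Needs the interpreter sentence? |
|---|---|---|
| English is the primary language | Yes | No |
| English is the native language, another language is now primary | Yes, through the word or | Possibly |
| English is neither primary nor native | No | Yes, if English is limited |

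The sentence can serve an eligible patient only in the second row, which is a narrow group and unlikely to be the one intended. For nearly everyone who would need an interpreter, criterion 3 already excludes participation.

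**The case against.** The strongest reply is that this is a wording error surrounded by intact safeguards. Section 4.4 requires an IRB-approved consent form that the participant reads, a verbal explanation of the study's purposes, procedures and risks, and a signature before any study procedure. It requires orientation questions and capacity questions, one of which asks the patient to restate what was just said about this study. All of this is done by physicians trained in taking consent. The paragraph on altered mental state relies on the capacity testing and mental status examination, not on the restatement of goals. The operative words ask for the basic goals of the study, and a physician who has just described a pain injection would probably notice that the parenthesis does not fit.

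Much of this stands, and it rules out several stronger readings that a reader might infer:

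- **That consent is given to, or recorded for, a different study, or is invalid.** Consent is documented by the signed form. At worst the check records a wrong goal inside a consent process for the right trial. The form is not among the documents available here, so nothing can be concluded about its content.
- **That the text was carried over from another protocol.** This is plausible, but the documents do not show where it came from.
- **That the check will in practice pass patients who misunderstand and fail those who understand.** This requires physicians to apply the parenthesis against what they have just explained. The documents give no evidence that they would.
- **That the interpreter sentence opens a route to enrolling ineligible patients.** A sentence on how the restatement may be made does not override the rule that all inclusion criteria must be met.

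What the reply does not do is correct the check. Staff who notice the error must depart from the written protocol to do the right thing, and an accurate answer to the open capacity question would not match the goal stated shortly afterwards.

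**Conclusion.** The point holds as an internal contradiction in an operative consent step. The goal named in the comprehension check is not an aim or endpoint of this trial, so the check as written cannot verify that a subject understands it. The interpreter allowance conflicts with criterion 3 for nearly every patient who would use it.

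The goal wording applies to every participant, about 400 as planned. The interpreter conflict concerns only the few who would need one. Randomization, endpoints, analysis, sample size and power are untouched. The harm is limited by the other consent safeguards, so this should be corrected but does not undermine the trial.

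The conclusion assumes that i.e. is meant in its ordinary sense and that the stated aims and endpoints are the intended ones. If bone healing were in fact an intended goal, the omission would lie in sections 2.2 to 2.4 and 6.2 instead, and nothing in the document suggests that.

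**What to change.** 1. Replace the parenthesis in the comprehension paragraph of section 4.4 with the trial's own goal: whether a surgical site injection during fracture surgery, compared with no injection, changes post-operative pain and narcotic use.
2. Reconcile the interpreter sentence with criterion 3. The simpler course is to delete the sentence. The alternative is to amend criterion 3. That has a larger cost, because section 3.1 relies on repeated follow-up calls and on telephone completion of the SMFA and the second APS-POQ, and the protocol describes no interpreter for those.
3. Check that any consent checklist or note template in use does not repeat the bone-healing wording.

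The cost of deleting the sentence and correcting the parenthesis is a short amendment, which section 9.2 requires the IRB to approve before it takes effect, and a notice to the staff who take consent. No statistical section needs to change.
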